4.2. Primary Endpoint Analyses

4.2.1. Definition of endpoint

The primary endpoint is the annualized rate of clinically significant exacerbations over the 52 weeks following randomisation.

Clinically significant exacerbations of asthma are defined as worsening of asthma requiring the use of systemic corticosteroids (IM, IV or oral) and/or hospitalisation and/or ED visit (see protocol Section 8.2.2). For all participants, IV or oral steroids (e.g., prednisone) for at least 3 days or a single IM CS dose is required. For participants on maintenance systemic CSs, at least double the existing maintenance dose for at least 3 days is required.

Exacerbations recorded in the eCRF are considered as verified clinically significant exacerbations and will be included in the primary analysis.

Exacerbations separated by less than 7 days will be treated as a continuation of the same exacerbation.

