4.11.2.1. Decision Rule

The interim analysis will be based on the predictive probability of meeting the end of study (program) success criteria (defined as statistical significance at a two-sided 5% alpha level in **both** studies 206713 and 213744). Should the predictive probability of success be less than or equal to 0.25 then the studies will be stopped for futility.

The futility rule:

Futility	Continue
Predictive probability (statistical	Predictive probability (statistical
significance two-sided 5%) in both	significance two-sided 5%) in both 206713
$206713 \& 213744) \le 0.25$	& 213744) > 0.25

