 - 1. The design matrix (Z) is multiplied with the set of posterior β samples and then back-transformed (exponentiated) to give expected annualised

exacerbation rate for each participant (μ_i) based on the interim data. Note: for participants yet to be randomised, and therefore without values observed for baseline covariates, bootstrapping from already randomised participants will be performed.

- 2. The expected exacerbation rate for the pre-interim and post-interim periods are calculated by multiplying μ_i by the pre-interim and post-interim times in the study for the participant: $\hat{y}_{i,1} = \mu_i \times t_{i,1}$ and $\hat{y}_{i,2} = \mu_i \times t_{i,2}$.
- 3. For the two periods (pre and post-interim), the number of exacerbations within each period is negative binomial. The distribution of one period conditional upon the other, within a participant, is also negative binomial [Keene, 2014]. The negative binomial parameters for the post-interim period are calculated for each participant and set of posteriors samples (iteration):

$$p_{i,2} = \frac{\frac{1}{k} + \hat{y}_{i,1}}{\frac{1}{k} + \hat{y}_{i,1} + \hat{y}_{i,2}}$$
$$k_{i,2} = k_1 + count_{i,1}$$

Where k_1 is the sampled dispersion parameter, $count_{i,1}$ is the number of exacerbations for participant *i* in period 1 (pre-interim), *i* is the participant and j=1,2 is the period (pre, post-interim).

Using these parameters, simulate a participant's number of clinically significant exacerbations for post-interim data for each set of posterior samples

- 4. The pre-interim observed data (one set) will be combined with each set of postinterim data (1000s of sets) to create 1000s of end of study datasets
 - 1. Each participant's exacerbation count will be the summation of pre-interim observed count (if the participant was randomised at least one month before the interim data cut) plus the post-interim simulated exacerbation count (if the participant did not complete before the interim).
 - 2. Each participant's length of time in the study will now be the assumed average length of time in the study, which is set at 0.86 years.
- 5. The primary analysis model is applied to each iteration (dataset), each study separately. The p-value for the treatment effect (rate ratio) will be calculated. For each iteration, if the success criteria (statistical significance at 5% two-sided level for both studies) is met then the iteration is marked as success (flag as 1), or if not then fail (flag as 0).

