4.11.2.3. Timing and Operating Characteristics

The proposed timing of the futility analysis is when approximately 675 participants have been randomised across the studies. At this time it is estimated that approximately 200 participants will have completed the studies and 500 received both doses (i.e. at least 6 months worth of data). The median follow-up time in the interim analysis is estimated to be 9 months with the information fraction for the primary endpoint estimated to be 60%, where information fraction is calculated as:

$$Information \ fraction = \frac{\sum_{i=1}^{n(interim)} length \ of \ time \ in \ study \ at \ interim_i}{\sum_{i=1}^{750} length \ of \ time \ expected \ in \ complete \ study_i}$$

Table 5 shows operating characteristics of the futility analysis for a range assumed true treatment effects when approximately 725 participants have been randomised (proposed interim timing). Operating characteristics were obtained by simulating 5,000 studies and following the steps in Section 4.11.2.2 for each simulated study. Operating characteristics are obtained from the aggregate of these simulations.

As this is a futility analysis and there is no opportunity to stop for efficacy the type 1 error (calculated under the null hypothesis of assumed rate ratio = 1) is controlled well below the 5% level. The power of each study is approximately 99%, compared with >99% in the scenario where there is no futility analysis (as described in the protocol). The

expected observed rate ratio at the interim to trigger futility is expected to be approximately 0.70.

Assumed treatment effect (rate ratio depemokimab vs. placebo)	Probability of success (statistical significance in both studies)	Power ¹ : 206713	Power1: 213744	Probability of futility
1	<0.01	<0.01	<0.01	0.98
0.9	0.01	0.04	0.02	0.94
0.8	0.08	0.18	0.13	0.76
0.7	0.37	0.50	0.44	0.42
0.6	0.78	0.85	0.82	0.11
0.5	0.98	0.98	0.98	0.01

Table 5 Operating Characteristics of Futility Analysis

¹ at two-sided 5% significance level for end of study test and incorporating the possibility of futility

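### The futility prediction gives every participant 0.86 years of exposure instead of their own time, which matters mainly if withdrawal differs between arms

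*SAP*

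**What the plan says.** SAP Section 4.11.2.1 defines success as "statistical significance at a two-sided 5% alpha level in" both 206713 and 213744. "Should the predictive probability of success be less than or equal to 0.25", the studies stop. Section 4.11.2 calls the rule binding, on condition that the IDMC finds no delayed onset of efficacy.

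Section 4.11.2.2 builds the predicted datasets. Step 4.1 gives each participant the observed pre-interim count, plus a simulated count "if the participant did not complete before the interim". Step 4.2 then sets the exposure of each participant to "the assumed average length of time in the study, which is set at 0.86 years", with no exception. Step 5 fits the primary model to each study and flags success on the p-value of the rate ratio.

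The post-interim time `t_i,2`, which drives the simulated counts, is given no value. The section also does not say whether participants who withdrew before the interim receive simulated events.

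The endpoint in Section 4.2.1 is the "annualized rate of clinically significant exacerbations over the 52 weeks following randomisation". The primary model in Section 4.2.2 uses the log of each participant's total time in study as its offset. Section 4.11.2.3 expects that "approximately 200 participants will have completed the studies" at the interim.

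**The concern.** The value 0.86 is a mean over completers and withdrawals. Using it for individuals discards times that are already in the interim database. A completer's one-year count is divided by 0.86 years. An early withdrawal's short count is spread over 0.86 years, unless events are simulated for the period after leaving. The first overstates that participant's rate and the second understates it. Neither matches the final analysis, which uses actual time.

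At stake is the predictive probability compared with 0.25, and so a recommendation that can end two pivotal studies.

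**Working it through.** **1. Where 0.86 comes from.** SAP Section 5.1.1 assumes a placebo rate of 1.18, rate ratio 0.5, dispersion 0.8, allocation 250:125 and 14% of participant-years missing, so mean exposure is 1 − 0.14 = 0.86. The variance of the log rate ratio is

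Var = [(1/t)(1/r0 + 1/(2·r1)) + 1.5k]/125 = [(1/0.86)(1/1.18 + 1/1.18) + 1.2]/125 = 0.02537, so SE = 0.159.

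Power = Φ(0.693/0.159 − 1.96) = 99.2%, against 99% stated. The smallest significant reduction corresponds to exp(−1.96 × 0.159) = 0.73, as stated. All 12 cells of the power table reproduce within 1 point. As a mean in a sample-size formula, 0.86 is sound.

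**2. Effect on one participant.** A completer's rate is multiplied by 1/0.86 = 1.163, an overstatement of 16.3%.

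**3. Effect on the test.** The model is log(mean count) = intercept + covariates + log(time). If time is the same constant for all, log(time) merges with the intercept, and the rate ratio, its SE and its p-value do not depend on the constant. Only variation in true exposure that the constant hides can matter, above all variation between arms.

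**4. Simulation with equal follow-up.** Setting: two studies of 375 at 2:1, 675 randomised, about 197 completers, about 500 with at least six months, exponential withdrawal with mean follow-up 0.86, and 200 predictive draws per dataset. Each predicted dataset was tested with 0.86 for all and with actual times. The middle columns show P(futility), 0.86 for all → actual times.

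| True RR | Datasets | Withdrawals left short | Withdrawals filled to 0.86 | SAP Table 5 |
|---|---|---|---|---|
| 1.0 | 60 | 1.00 → 1.00 | 1.00 → 1.00 | 0.98 |
| 0.8 | 120 | 0.78 → 0.74 | 0.708 → 0.708 | 0.76 |
| 0.7 | 200 | 0.455 → 0.425 | 0.395 → 0.390 | 0.42 |
| 0.6 | 120 | 0.108 → 0.108 | 0.075 → 0.083 | 0.11 |
| 0.5 | 60 | 0.017 → 0.000 | 0.000 → 0.000 | 0.01 |

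- Left short, as written, agrees with Table 5 within simulation error. The Monte Carlo SE at RR 0.7 is √(0.455 × 0.545/200) = 0.035, although the two offsets are compared on the same datasets.
- Left short: the mean absolute change in predictive probability is at most 0.05, and 0–6% of decisions flip.
- Filled to 0.86, where almost only completers are mismatched: the mean change is about 0.01, and 0–2.5% of decisions flip.
- The sign depends on the reading. Relative to actual times with no events added after withdrawal (0.74, 0.425 and 0.108 at RR 0.8, 0.7 and 0.6), the filled version as written gives less stopping (0.708, 0.395 and 0.075). The left-short version gives equal or more (0.78, 0.455 and 0.108).
- If everyone is filled to one year, offsets of 0.86 and 1.0 give identical p-values. That dataset assumes no withdrawal, however, and P(futility) at RR 0.7 is 0.355.

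**5. Unequal follow-up at RR 0.7.** The documents give no follow-up by arm, so these values are assumptions. Both keep the overall mean at 0.86: (0.80 + 2 × 0.89)/3 = 0.86 and (0.92 + 2 × 0.83)/3 = 0.86. With a common 0.86, counts that reflect the true times distort the apparent rate ratio by 0.89/0.80 = 1.11 in the first case and 0.83/0.92 = 0.90 in the second. There were 150 datasets per case.

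| Mean follow-up, placebo / active | Withdrawals | P(futility), 0.86 for all | P(futility), actual times | Decisions flipped |
|---|---|---|---|---|
| 0.80 / 0.89 | left short | 0.68 | 0.46 | 22%, all to stop |
| 0.80 / 0.89 | filled to 0.86 | 0.42 | 0.38 | 4%, all to stop |
| 0.92 / 0.83 | left short | 0.30 | 0.41 | 11%, all to continue |
| 0.92 / 0.83 | filled to 0.86 | 0.37 | 0.39 | 4%, mostly to continue |

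The SE of the 22% is √(0.22 × 0.78/150) = 0.034.

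**The case against.** The strongest reply is that success depends on the p-value of a rate ratio. Completers occur in both arms, so their 16% largely cancels. This stands. A reader might infer from the 16% that the predictive probability is distorted to a similar degree, and steps 3 and 4 show that it is not.

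The second reply is that Table 5 was obtained by following these same steps, so it describes the rule as written, approximation included. This also stands: nothing here shows Table 5 to be wrong. Its limit is that good operating characteristics under equal withdrawal would not reveal the behaviour in step 5. The documents do not say what withdrawal pattern Table 5 assumed.

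A reader might also infer that ongoing participants already past 0.86 years have negative remaining time. That requires `t_i,2` to be 0.86 minus elapsed time. The SAP does not define it so; if it runs to 52 weeks, the problem does not arise.

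Nor do the documents support reading this as an unconditional stop or as a threat to type I error. Stopping depends on the IDMC's view of delayed onset, there is no efficacy stop, and the final analysis still uses actual time.

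**Conclusion.** The point holds as a mismatch between the predicted and the planned analysis. No reading of the undefined `t_i,2` fully removes it: filling everyone to one year makes the constant harmless but assumes away the 14% loss. With equal follow-up the consequence is small, about 0.00 to 0.04 in P(futility) with no fixed sign. It becomes material if withdrawal differs by arm and withdrawals keep a short count over 0.86 years: 22% or 11% of decisions flip at RR 0.7 in the two assumed cases. With withdrawals filled to 0.86, about 4% flip in either case.

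These figures rest on assumptions outside the documents: exponential withdrawal, the accrual shape (information fraction 0.64–0.65 and median follow-up 0.66 years, against 60% and 9 months stated), study 206713 being of the same size and design (750 − 375 = 375), a normal approximation to the posterior, no baseline covariates, and the by-arm follow-up values. The simulation used 675 randomised, while Table 5 is described for about 725. It also used 1/k plus the observed count as the conditional size parameter, where the SAP prints k plus the count.

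**What to change.** Rewrite step 4.2 of SAP Section 4.11.2.2:

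- For participants who completed or withdrew before the interim, use observed time, and simulate no events for withdrawals.
- For ongoing and not-yet-randomised participants, use observed plus predicted remaining time up to 52 weeks, with predicted withdrawal consistent with the assumed 14% of participant-years lost.
- Define `t_i,2` from these times, and use the same times in the offset at step 5.
- Re-run Table 5, preferably adding a scenario with unequal withdrawal.

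The cost is a few lines of code and a re-run. Table 5 figures may move by a few points in either direction. If the interim program already works this way, only the text needs correcting.

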4.11.2.3. Timing and Operating Characteristics

The proposed timing of the futility analysis is when approximately 675 participants have been randomised across the studies. At this time it is estimated that approximately 200 participants will have completed the studies and 500 received both doses (i.e. at least 6 months worth of data). The median follow-up time in the interim analysis is estimated to be 9 months with the information fraction for the primary endpoint estimated to be 60%, where information fraction is calculated as:

$$Information \ fraction = \frac{\sum_{i=1}^{n(interim)} length \ of \ time \ in \ study \ at \ interim_i}{\sum_{i=1}^{750} length \ of \ time \ expected \ in \ complete \ study_i}$$

Table 5 shows operating characteristics of the futility analysis for a range assumed true treatment effects when approximately 725 participants have been randomised (proposed interim timing). Operating characteristics were obtained by simulating 5,000 studies and following the steps in Section 4.11.2.2 for each simulated study. Operating characteristics are obtained from the aggregate of these simulations.

As this is a futility analysis and there is no opportunity to stop for efficacy the type 1 error (calculated under the null hypothesis of assumed rate ratio = 1) is controlled well below the 5% level. The power of each study is approximately 99%, compared with >99% in the scenario where there is no futility analysis (as described in the protocol). The

expected observed rate ratio at the interim to trigger futility is expected to be approximately 0.70.

Assumed treatment effect (rate ratio depemokimab vs. placebo)	Probability of success (statistical significance in both studies)	Power ¹ : 206713	Power1: 213744	Probability of futility
1	<0.01	<0.01	<0.01	0.98
0.9	0.01	0.04	0.02	0.94
0.8	0.08	0.18	0.13	0.76
0.7	0.37	0.50	0.44	0.42
0.6	0.78	0.85	0.82	0.11
0.5	0.98	0.98	0.98	0.01

Table 5 Operating Characteristics of Futility Analysis

¹ at two-sided 5% significance level for end of study test and incorporating the possibility of futility

4.11.2.4. Outputs

- An interim analysis-specific output presenting the predicted probability of success at the interim
- An interim analysis-specific output presenting model-adjusted annualised exacerbation rate ratio for depemokimab compared to placebo by time period (< 3 months since randomisation, 3-6, 6-9, 9-12)
- Kaplan-Meier plot of time to first clinically significant exacerbation
- Primary analysis summary table for each study. The primary analysis will be conducted on the interim data and provide model-adjusted estimates as a supportive output.
- Summary of Subject Disposition and Reasons for Study Withdrawal
- Summary of Demographic Characteristics
- Summary of Time in Study

4.11.2.5. Decision Making

The outputs from the interim analysis will be forwarded from the SDAC to the IDMC. As the stopping rule is binding, the decision will be communicated from the SDAC to the IDMC and then to GSK following agreement from the IDMC.

4.12. Changes to Protocol Defined Analyses

Changes from the originally planned statistical analysis specified in the protocol amendment 2 (Dated: 08-APR-2022) and its rationale are summarised as below.

Substantial validation work has been conducted on the ADSD/ANSD PRO measures since the original protocol and SAP were finalised. These measures will provide additional treatment benefit information and could be included in the label for treatment

decision making. Consequently, and following additional regulatory agency feedback, ADSD/ANSD change from baseline at week 52 endpoints have been added as secondary endpoints and into the hierarchy. In addition, ADSD and ANSD responders have been added as other endpoints.

5. SAMPLE SIZE DETERMINATION

Approximately 540 participants with severe uncontrolled asthma with an eosinophilic phenotype will be screened to ensure the randomisation of 375 participants in a 2:1 ratio to GSK3511294 (n=250) and matching placebo (n=125).

5.1. Sample Size Assumptions

A sample size of 375 participants (2:1 GSK3511294 to placebo allocation ratio) is based on sufficient power to conclude superiority on primary and key secondary endpoints.

5.1.1. Primary Endpoint

The assumed true annualised rate of exacerbations in the placebo arm is 1.18. Based on an assumed true treatment difference of a 50% reduction in annualised exacerbation rate between GSK3511294 + SoC and placebo + SoC, a sample size of 375 randomised participants (250 to GSK3511294, 125 to placebo) will provide 99% power for the primary endpoint at a 5% two-sided significance level [PASS, 2020].

The assumptions for the placebo rate and treatment effect are median values from an elicitation exercise which used Phase 3 anti-IL-5/5R historical data (~50% reduction in exacerbations) and expert opinion. The sample size is based also on an assumption of 0.8 for the dispersion parameter which was observed in two mepolizumab studies [Pavord, 2012; Ortega, 2014]. It was assumed that 14% of participant-years data will be missing due to study withdrawal, which is also consistent with mepolizumab studies.

Based on the assumptions above, the minimum observed treatment difference estimated to result in significance at the 5% two-sided significance level is a 27% reduction in exacerbations for GSK3511294 + SoC compared with placebo + SoC (rate ratio of 0.73).

5.1.2. Secondary Endpoints

Table 6 describes the assumptions and power values for two key secondary endpoints. The assumptions are obtained from the Phase 3 mepolizumab studies [Pavord, 2012; Ortega, 2014; Chupp, 2017].

Table 6 Power Calculations for Key Secondary Endpoints

Endpoint	Assumed treatment difference (GSK3511294 + SoC vs. placebo + SoC)	Standard deviation	Power
Change from baseline in SGRQ total score at Week 52	-7	17	96%
Change from baseline in ACQ-5 score at Week 52	-0.35	1.1	83%

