9.2.1.2. Secondary Endpoints

[Table 3](#) describes the assumptions and power values for two key secondary endpoints. The assumptions are obtained from the Phase 3 mepolizumab studies [[Pavord](#), 2012; [Ortega](#), 2014; [Chupp](#), 2017].

Table 3 Power Calculations for Key Secondary Endpoints

Endpoint	Assumed treatment difference (GSK3511294 + SoC vs. placebo + SoC)	Standard deviation	Power
Change from baseline in SGRQ total score at Week 52	-7	17	96%
Change from baseline in ACQ-5 score at Week 52	-0.35	1.1	83%

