4. STATISTICAL ANALYSES

4.1. General Considerations

4.1.1. General Methodology

The Full Analysis Set (FAS) will be used for all Study Population, Efficacy, Immunogenicity and PD analyses, unless otherwise stated. The Safety analysis set will be used for safety analyses, unless otherwise stated. PK analysis sets will be used for PK data analysis. FAS-Japan, Safety-Japan and PK-Japan will be used for Japan outputs. The Output and Programming Specification (OPS) document will provide more details.

Confidence intervals will use 95% confidence intervals (CI) unless otherwise specified.

Unless otherwise specified, continuous data will be summarised using descriptive statistics: n, mean, standard deviation (std), median, minimum and maximum. Categorical data will be summarised as the number and percentage of participants in each category.

For endpoints that are formally modelled, summary statistics will be provided. In the statistical analysis where covariates are included in the modelling, the following approach will be applied:

- The covariate of exacerbation history is classified as 2, 3, 4+. In the event that exacerbation history is <2, it will be included in the category of '2'.
- For the covariate of baseline pre-bronchodilator % predicted FEV1, screening prebronchodilator % predicted FEV1 will be used if baseline value is missing. If both sreeening and baseline pre-bronchodilator % predicted FEV1 are missing, a missing value will be assigned for this covariate.

Where statistical models are used, if there are important departures from the distributional assumptions, transformations of covariates or alternative models may be explored as supporting analyses.

Randomisation is stratified based on baseline ICS dose (medium or high). All statistical models will include this stratum as a covariate. In the case of wrong stratification assigned at the time of randomization, the analyses will be performed based on the data collected in the CRF, not the assigned stratum at randomization.

Assessments collected at withdrawal visit will be included in summary tables but won't be included in any statistical analysis.

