4.3.2. Main analytical approach for SGRQ total score, ACQ-5 score and pre-bronchodilator FEV₁

Secondary Endpoints Analyses
Endpoint(s)
 Change from baseline in SGRQ total score at Week 52 Change from baseline in ACQ-5 score at Week 52 Change from baseline in pre-bronchodilator FEV1 at Week 52
Model Specification
 Mixed Models Repeated Measures (MMRM) model. Terms in the model: Response: SGRQ Total score or ACQ-5 score or pre-bronchodilator FEV1 at each visit. Categorical: treatment group, exacerbation, baseline ICS dose (medium or high), exacerbation history (variable (2, 3, 4+)), geographical region, visit Continuous: baseline (SGRQ Total score, or ACQ-5 score, or baseline pre-bronchodilator FEV1), baseline pre-
 bronchodilator % predicted FEV1 (for SGRQ total score and ACQ-5 endpoints only) Interaction: baseline*visit, treatment group*visit Repeated: visit The MMRM analysis for SGRQ total scores will include data collected at Weeks 4, 12, 26, 40 and 52.
 The MMRM analysis for ACQ-5 score will include data collected at Weeks 2, 4, 8, 12, 16, 20, 24, 26, 28, 32, 36, 40, 44, 48 and 52. In the event the model fails to run due to too many assessment timepoints, timepoints included in the analysis may be reduced by keeping the timepoints of most interest. Suggested order for dropping timepoints is week 44, 20, 36, 16, 32, 8, 48, 24, 28.
 The MMRM analysis for pre-bronchodilator FEV1 will include data collected at Weeks 26 and 52. The model will be fit with an unstructured variance-covariance matrix.
 The Kenward and Roger method (KR) for approximating the denominator degrees of freedom and correcting for bias in the estimated variance-covariance of the fixed effects will be used. In the event the model fails to run using the KR method, then the residual method will be used instead. In the event the model fails to run using residual method and assessments are from many timepoints, timepoints included in the analysis may be reduced by keeping the timepoints/intervals of most interest. Baseline is defined in Section 4.1.2
 Two models will be fitted; one with a response variable of change from baseline and one with the response variable as the raw value.
Model Checking & Diagnostics

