 Distributional assumptions underlying the model used for analysis will be examined by obtaining a normal probability plot of the residuals and a plot of the residuals versus the fitted values (i.e. checking the normality assumption and constant variance assumption of the model respectively) to gain confidence

that the model assumptions are reasonable.
Ilts Presentation
Least-square (LS) means and LS mean change from baseline values for each treatment group will be presented with their associated standard errors as well as 95% CIs. The estimated treatment difference along with corresponding standard error, 95% CI and P-values for each visit will be presented. The LS mean treatment differences (and associated 95% CIs) for all visits will also be presented graphically. SGRQ total scores, ACQ-5 score and pre-bronchodilator FEV1 (absolute value and changes from baseline) wil also be summarised by treatment group and visit.
Handling of missing data and data excluded due to intercurrent events
For participants that discontinue study intervention due to reasons related to the COVID-19 pandemic, the observed data for the period following this intercurrent event will be excluded from the analysis. Data for this period will be assumed MAR (based on all data included in the analysis under the current estimand strategy). For participants that withdraw from the study, preventing assessment of the endpoint, the data for the period
following withdrawal will be assumed MAR (using data collected under the proposed estimand strategy).
tional Analysis
same secondary endpoint analyses will be performed using FAS-modified analysis set
group Analysis by baseline eosinophil subgroup 1 (<0.15, >=0.15), by baseline eosinophil subgroup 2 (<0.30, >=0.30) and by baseline ACQ-5 (<1.5, >=1.5) subgroup analyses will be performed for FAS analysis set . For subgroup analysis, subgroup, subgroup*treatment group and subgroup*visit*treatment group terms will be included in each of subgroup analysis model.
In the event the subgroup analysis model fails to converge, model simplification methods may be addressed (i.e. adjusting covariate structure, streamlining timepoints, combining subgroups, running model separately for subgroup). A forest plot will be produced to present estimated treatment differences and 95% CIs at week 52 including all subgroups (including P-value for subgroup*treatment group interaction)

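### The stated secondary power (SGRQ 96%, ACQ-5 83%) allows for no missing data, unlike the primary power; at 14% loss with the printed SDs it is about 94% and 77%

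*SAP*

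**What the plan says.** SAP Section 5.1 states that the sample size of 375, randomised 2:1, "is based on sufficient power to conclude superiority on primary and key secondary endpoints". For the primary endpoint, Section 5.1.1 adds a withdrawal assumption: "It was assumed that 14% of participant-years data will be missing due to study withdrawal, which is also consistent with mepolizumab studies". The futility methodology in Section 4.11.2.2 uses the same figure as a follow-up time: "the assumed average length of time in the study, which is set at 0.86 years".

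For the secondary endpoints, "Table 6 describes the assumptions and power values for two key secondary endpoints" (SAP Section 5.1.2). Protocol Section 9.2.1.2 has the same sentence and the same values in Table 3:

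| Endpoint (change at Week 52) | Difference | SD | Power |
|---|---|---|---|
| SGRQ total score | -7 | 17 | 96% |
| ACQ-5 score | -0.35 | 1.1 | 83% |

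Neither table gives a loss allowance, an analysed number or a formula. Neither says whether the SDs are raw or model-adjusted.

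The analysis section does expect missing Week 52 values. SAP Section 4.3.2 sets a missing-at-random rule that begins "For participants that withdraw from the study, preventing assessment of the endpoint". SAP Section 4.1.1 says: "Assessments collected at withdrawal visit will be included in summary tables but won't be included in any statistical analysis".

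**The concern.** The primary and secondary powers are presented together as support for one sample size, yet only the primary power appears to include the assumed withdrawal. A reader would take 83% for ACQ-5 as the power under the plan's own assumptions.

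ACQ-5 is third of the seven steps in the fixed sequence (SAP Section 2.1). If it is tested and is not significant, FEV1, ANSD, ADSD and the hospitalisation/ED exacerbation rate cannot be tested. An overstated ACQ-5 power therefore understates the chance that the sequence stops there.

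**Working it through.** **Inputs.** Two-sided 5% (SAP Section 2); 250 vs 125 (SAP Section 5); differences and SDs from SAP Table 6; 14% of participant-years lost, dispersion 0.8 and placebo rate 1.18 (SAP Section 5.1.1).

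**1. Reproduce Table 6.** The formula is inferred, because none is printed:

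Power = Φ( δ / [SD·√(1/n₁ + 1/n₀)] − 1.96 )

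With 250 vs 125:

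- SGRQ: SE = 17·√(1/250 + 1/125) = 1.862; 7/1.862 = 3.759; Φ(1.799) = 96.4%.
- ACQ-5: SE = 1.1·√(1/250 + 1/125) = 0.1205; 0.35/0.1205 = 2.905; Φ(0.945) = 82.8%.

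These round to the printed 96% and 83%. A t-based version gives 96.3% and 82.6%.

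**2. How much loss the printed figures can absorb.** SGRQ still rounds to 96% down to 355 of 375 participants (5.4% loss). ACQ-5 rounds to 83% only down to 373 of 375 (0.7% loss). Neither reaches 14%. To keep the printed powers at 14% loss, the SDs would have to be about 16.0 and 1.02, which do not round to 17 and 1.1.

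**3. Confirm that the primary power includes the loss.** For a negative binomial Wald test on the log rate ratio, with placebo rate λ, rate ratio RR and follow-up t in years:

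Var = [1/(λt) + 0.8]/125 + [1/(λ·RR·t) + 0.8]/250

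Power = Φ( |ln RR|/√Var − 1.96 )

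Placebo rates 1.0 / 1.1 / 1.18 / 1.3:

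| Reduction | Printed, SAP Table 7 | t = 0.86 | t = 1.0 |
|---|---|---|---|
| 30% | 61 / 63 / 65 / 67 | 60.7 / 63.2 / 65.0 / 67.4 | 64.7 / 67.0 / 68.7 / 71.0 |
| 40% | 88 / 90 / 91 / 92 | 87.9 / 89.7 / 90.9 / 92.4 | 90.6 / 92.1 / 93.1 / 94.2 |

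Only 0.86 years fits. The smallest significant effect agrees: at a 50% reduction and rate 1.18, the threshold rate ratio is 0.732 at 0.86 years (printed 0.73) and 0.742 at 1 year.

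**4. What 14% of participant-years implies at Week 52.** The loss is 0.14 × 375 = 52.5 participant-years. One participant can lose at most one year, so at least 53 must withdraw, and at most 375 − 53 = 322 have Week 52 data. A withdrawal visit that falls at Week 52 (Protocol Section 7.2) does not add to this, because SAP Section 4.1.1 keeps withdrawal-visit data out of the statistical analyses.

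**5. Power with 14% absent at Week 52.** With 250 × 0.86 = 215 and 125 × 0.86 = 107.5:

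- SGRQ: SE = 2.008; 7/2.008 = 3.486; Φ(1.526) = 93.6%.
- ACQ-5: SE = 0.1299; 0.35/0.1299 = 2.694; Φ(0.734) = 76.8%.

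Whole numbers (215 vs 107) give 93.6% and 76.7%. At 5% loss the values are 95.6% and 80.8%.

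**6. Effect of covariate adjustment, if SD 1.1 is a raw change-score SD.** ACQ-5 power at 215 vs 107.5:

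| Variance reduction | ACQ-5 power |
|---|---|
| 0% | 76.8% |
| 10% | 81.0% |
| 14% | 82.8% |
| 15% | 83.2% |
| 20% | 85.4% |

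A 14% reduction exactly cancels a 14% loss, because (1 − 0.14)/0.86 = 1.

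**The case against.** The strongest reply is that Table 6 contains no miscalculation. It is correct for its printed inputs at the randomised number. The 14% is stated only for the primary endpoint, in participant-years, and Section 5.1.2 never claims to use it.

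The figures of 94% and 77% also describe a completer comparison that the SAP does not plan. Section 4.3.2 specifies an MMRM with a baseline term ("Continuous: baseline (SGRQ Total score, or ACQ-5 score, or baseline pre-bronchodilator FEV1"), other covariates and earlier visits, so participants who withdraw still contribute. Suppose the SDs are raw and the baseline and Week 52 variances are equal (an assumption the documents do not give). Adjusting for baseline then cuts the variance by (1 − r)/2, where r is the correlation between baseline and Week 52. The 14% loss is recovered in full when r is 0.72 or lower, and at r = 0.5 ACQ-5 power would be 87.5%. There is also no numeric power target for secondary endpoints, and restating a planning figure changes no analysis.

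Much of this stands as a limit on the size. It cannot be shown from the documents that 77% is the power the MMRM will have, and SGRQ stays well powered either way. It does not remove the inconsistency. The plan claims no covariate gain, and if the SDs are already adjusted that gain is not available. A reader cannot tell that 83% depends either on essentially complete Week 52 data or on an unstated gain. Nor does the change of unit favour the printed figures: 14% of participant-years implies at least 14% of participants without Week 52 data.

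**Conclusion.** The concern holds. The printed 96% and 83% match complete Week 52 data, while the primary power for the same 375 participants includes the 14% loss. Under that loss and the printed SDs, power is about 94% for SGRQ and 77% for ACQ-5, a drop of roughly 3 and 6 percentage points. The chance of a non-significant ACQ-5 test, if it is reached, goes from 17% to about 23%.

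This rests on three assumptions: the inferred two-sample formula, the printed SDs being the analysis SDs, and 14% of participants lacking Week 52 data. The last is the smallest share compatible with the stated loss. If withdrawals are spread over the year, fewer participants complete and completer power is lower, with part recovered by the MMRM; the documents give no withdrawal timing, so no figure is claimed for that case. If the SDs are raw, covariate adjustment raises power and could offset the loss. Primary power is unaffected.

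**What to change.** In SAP Table 6 and protocol Table 3:

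- Restate power under the 14% withdrawal assumption as about 94% (SGRQ) and 77% (ACQ-5), or keep 96% and 83% labelled as assuming no missing data, with those values beside them.
- State the assumed number with Week 52 data (at most about 322 of 375).
- State whether SDs 17 and 1.1 are raw or model-adjusted. If they are raw and a covariate gain is relied on, give its assumed size and the resulting power.

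The change is to the wording of two tables. Sample size, tests and hierarchy stay as they are. The only downside is a less favourable stated power, mainly for ACQ-5.
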